# 2. SYNOPSIS

Phase of Clinical Study Number of Sites Study Objective Too	OTX-DP (dexamethasone ophthalmic insert, 0.4mg) or PV (Placebo Vehicle)  Phase 3  Approximately 4 investigative sites in the United States  To evaluate the efficacy and safety of OTX-DP as a dexamethasone ophthalmic insert when placed in the canaliculus of the eyelid for the treatment of the signs and symptoms of allergic conjunctivitis.  OTX-DP is a resorbable hydrogel intracanalicular insert containing an anti-inflammatory glucocorticoid agonist. The insert is designed to be placed into the punctum and is retained in the canaliculus for the entire drug delivery duration. Over time, the insert softens and liquefies via
Number of Sites  Study Objective  To the state of the sta	Approximately 4 investigative sites in the United States  To evaluate the efficacy and safety of OTX-DP as a dexamethasone ophthalmic insert when placed in the canaliculus of the eyelid for the treatment of the signs and symptoms of allergic conjunctivitis.  OTX-DP is a resorbable hydrogel intracanalicular insert containing an anti-inflammatory glucocorticoid agonist. The insert is designed to be placed into the punctum and is retained in the canaliculus for the entire drug delivery duration. Over time, the insert softens and liquefies via
Study Objective To o	To evaluate the efficacy and safety of OTX-DP as a dexamethasone ophthalmic insert when placed in the canaliculus of the eyelid for the treatment of the signs and symptoms of allergic conjunctivitis.  OTX-DP is a resorbable hydrogel intracanalicular insert containing an anti-inflammatory glucocorticoid agonist. The insert is designed to be placed into the punctum and is retained in the canaliculus for the entire drug delivery duration. Over time, the insert softens and liquefies via
o tı	ophthalmic insert when placed in the canaliculus of the eyelid for the treatment of the signs and symptoms of allergic conjunctivitis.  OTX-DP is a resorbable hydrogel intracanalicular insert containing an anti-inflammatory glucocorticoid agonist. The insert is designed to be placed into the punctum and is retained in the canaliculus for the entire drug delivery duration. Over time, the insert softens and liquefies via
	anti-inflammatory glucocorticoid agonist. The insert is designed to be placed into the punctum and is retained in the canaliculus for the entire drug delivery duration. Over time, the insert softens and liquefies via

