# 6.3. Subject Enrollment

All subjects screened for the study who sign a consent form will be assigned a 5-digit Screening number which will be entered in the Screening and Enrollment Log. Screening numbers will be assigned in sequential order beginning with SXX001 where XX is a 2-digit site number.

Once a subject meets all qualification criteria, they will be randomly assigned to masked treatment using a 1:1 (OTX-DP: PV) assignment ratio. Subjects will be randomized on Visit 4b (Day 1) by assignment of the lowest 4-digit randomization number available at the investigative site, starting with RXX01, where XX is a 2-digit site number. No product numbers will be skipped or omitted. The investigational product will be inserted per the procedures outlined in Appendix G.

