# 8.6. Visit 4b (Day 1): Randomization/Insertion of OTX-DP or PV

- *Update of Medical/Medication History*
- Enrollment and Randomization: Subjects who meet entry criteria and qualify to continue in the study will be enrolled and randomly assigned to undergo the insertion of either OTX-DP or PV. Subjects will be assigned the lowest 4-digit randomization number available, starting with RXX01, where XX is a 2-digit site number. No randomization numbers will be skipped or omitted.
- Insertion of OTX-DP or PV: The Investigator will either insert OTX-DP or PV bilaterally based on the randomization schedule and according to the procedures outlined in Appendix G. The time of insertion will be recorded.
- Visualization of OTX-DP or PV: The Investigator will visualize correct placement of the intracanalicular inserts according to the procedures outlined in Appendix G.
- Adverse Event Query: Adverse Events will be monitored after the initial attempt of
  insertion of OTX-DP or PV. All adverse events will be promptly reviewed by the
  investigator for accuracy and completeness. All adverse events will be documented on the
  appropriate eCRF.

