### 9.9.2. Unmasking for Medical Emergencies

In the case of a medical emergency or occurrence of an SAE, the randomization code may be unmasked and made available to the Investigator, Sponsor, and/or other study personnel involved in the conduct of the study. In the absence of medical need, the randomization code will not be available to the above individuals until after the study is completed and the database is locked.

CLN-Protocol-0052 Page 38 of 61

In the event of a medical need, the Investigator will treat each subject, as medically required. If the Investigator feels it is necessary to unmask a subject's treatment assignment after an emergency, the Investigator may call the Medical Monitor and notify the Sponsor. The treatment assignment will be revealed on a subject-by-subject basis with the approval of the Medical Monitor and Sponsor, this leaving the masking of the remaining subjects intact.

The site will receive one emergency unmasking envelope for every product received and the envelopes should be stored in a secured location. The envelopes and product will both be labeled with the same randomization number. The envelopes are sealed and contain the unmasked treatment information for the corresponding study product.

Ocular Therapeutix will make the final determination if the unmasking request will be granted. Once the unmasking request is granted the investigator or designee should identify and retrieve the emergency unmasking envelope for the given subject. The emergency unmasking envelope should be opened by the designated site personnel. The investigator must also indicate in source documents and in the eCRF that the mask was broken and provide the date, time, and reason for breaking the mask. Any AE or SAE associated with breaking the mask must be recorded and reported as specified in this protocol.

Subjects will have the investigational product removed immediately if treatment assignment is unmasked.

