## **10.7.** General Imputation Methods

Missing data for the primary efficacy variable will be imputed using Markov Chain Monte Carlo (MCMC) multiple imputation techniques on the ITT population, producing twenty "complete" (imputed) datasets which will then be analyzed separately. Results from the separate analyses on the twenty "complete" datasets will be combined for presentation through the use of SAS PROC

CLN-Protocol-0052 Page **41** of **61** 

MIANALYZE. A separate imputation model will be fit for each time point. The model will include variables for treatment, baseline measure, and response measure.

For sensitivity analysis, the ITT population will also be analyzed using the following:

- Observed data only
- Last observation carried forward (LOCF)
- Worst case observation (WCO)
- Baseline observation carried forward (BOCF)

For the LOCF imputation, only post-challenge observations within the same visit will be carried forward. Therefore, there must be post-challenge values available at post-baseline visits to implement LOCF, as pre-challenge values will not be carried forward to post-challenge values and the prior visit values will not be carried forward to the following visit values. Missing values post-challenge will be carried forward from the last observed time point within the same visit, i.e., a missing 5-minute observation at Visit 5b will be imputed from the 3-minute observation from Visit 5b, etc.

For the WCO imputation, missing data due to a subject being prescribed anti-inflammatory or antiallergy medication will be imputed using the worst possible outcome (maximum observed value) from the subject's treatment group, starting at the first time point at which a subject takes an antiinflammatory or anti-allergy medication.

For the BOCF imputation, missing data post-baseline will be imputed with the corresponding time point baseline data from Visit 4a.

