### 10.8. Primary Efficacy Analyses

The primary efficacy endpoint is ocular itching assessed at  $3(\pm 1)$ ,  $5(\pm 1)$ ,  $7(\pm 1)$  minutes post- CAC® (0-4 scale, allowing half unit increments) at Visit 6b (Day 8; 7 days post-insertion; 8 hours from Visit 6a). The average of each subject's eyes at each post-CAC® time point will be used as the unit of analysis for ocular itching. Ocular itching will be analyzed using an ANCOVA model for each post-CAC® time point at Visit 6b, with the time appropriate post- CAC® scores at Visit 4a as a covariate and treatment group as the sole factor (OTX-DP compared to PV). Two-sample t-tests will be used as unadjusted sensitivity analyses at each

post-CAC® time point, as well as a non-parametric Wilcoxon rank sum tests (OTX-DP compared to PV). At each post-CAC® time point, a two-sided significance level of  $\alpha = 0.05$  will be used to determine statistical significance of treatment differences.

The primary efficacy analyses will be conducted on the intent-to-treat (ITT) population using the multiple imputation MCMC method for missing data as described previously. Sensitivity or supportive analyses will be performed on the ITT population using observed data only and the LOCF, BOCF and WCO methods. The PP population will also be analyzed using observed data only as a sensitivity analysis.

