### 10.9. Secondary Efficacy Analyses

Analyses will be performed on quantitative secondary endpoints in a manner similar to the primary endpoint. Qualitative measures will be analyzed using a Fisher's exact test or Chi- Square test as appropriate (OTX-DP compared to PV). Secondary endpoints include ocular itching (except at Visit 6b at  $3(\pm 1)$ ,  $5(\pm 1)$ , and  $7(\pm 1)$  minutes post-CAC), conjunctival redness, episcleral and ciliary redness, chemosis, eyelid swelling, tearing/watery eyes, rhinorrhea, nasal pruritus, ear or palate pruritus, nasal congestion, and a composite score (analyzed as a qualitative measure determined as the presence or absence of at least one nasal symptom [present/absent], and as a quantitative measure calculated as

CLN-Protocol-0052 Page **42** of **61** 

the sum of the four component symptom scores [ranging from 0 to 16]). The secondary endpoints will be analyzed for the ITT population with observed data only and for the PP population with observed data only.

In addition, quantitative analyses will include ANCOVA models which will be run at each visit, with treatment, time point, and time appropriate baseline as covariates for adjustment (accounting for repeated measurements). Least Square Means (LS Means) for each treatment, the corresponding 95% confidence intervals (CIs), and the estimated treatment difference between OTX-DP and PV will be calculated from these ANCOVA models.

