12.1 Primary Analysis

The primary efficacy variable is ocular itching evaluated by the subject at $3(\pm 1)$, $5(\pm 1)$, and $7(\pm 1)$ minutes post-CAC at Visit 6b (Day 8; 8 hours from Visit 6a). Ocular itching will be evaluated using the following Ora CalibraTM CAC Ocular Itching Scale as defined in Appendix A.

The average of each subject's eyes' itching score at each post-CAC time point will be used as the unit of analysis for ocular itching.

The primary analysis of ocular itching will be performed on the ITT population with MCMC multiple imputation methodology for missing data using an ANCOVA model for each post-CAC time point at Visit 6b, with the time appropriate post-CAC itching scores at Visit 4a as a covariate and treatment group as the sole factor.

For multiple imputations using MCMC, twenty "complete" (imputed) datasets will be produced and analyzed. Results from the analyses on the twenty "complete" datasets will be combined for presentation using SAS PROC MIANALYZE.

A separate imputation model will be fit for each visit and time point. The imputation model will include variables for treatment, baseline measure (the time appropriate post-CAC scores at Visit 4a), and response measure.

The following SAS code will be used to produce twenty "complete" datasets:

```
PROC MI DATA = INDATA SEED = 59411 NIMPUTE = 20 OUT =
OUTDATA1 MINIMUM=. 0 0 MAXIMUM=. 4 4 ROUND =. 0.25 0.25;
BY VISIT TIME;
MCMC INITIAL = EM;
VAR TREATMENT BASELINE SCORE;
RUN;
```

where

- INDATA is the name of the input dataset;
- OUTDATA1 is the name of the output dataset;
- TREATMENT is the name of the treatment group variable in numeric format;
- BASELINE is the time appropriate post-CAC scores at Visit 4a; and
- SCORE is the average (of right eye [OD] and left eye [OS] for each subject) ocular itching score.

After obtaining twenty "complete" datasets, the following SAS code will be employed to run the analysis of covariance (ANCOVA) models by time point on each dataset:

```
ODS OUTPUT SOLUTIONF = MIXPARMS LSMEANS = LS DIFFS = DIFF;
PROC MIXED DATA = OUTDATA1;
BY VISIT TIME _IMPUTATION_;
CLASS TREATMENT;
MODEL SCORE = BASELINE TREATMENT / SOLUTION;
LSMEANS TREATMENT / PDIFF CL;
RUN;
```

where

- *SUBJID* is the subject ID number;

- BASELINE is the time appropriate post-CAC scores at Visit 4a;
- VISIT is the visit; and
- *TIME* is the time point.

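### Randomisation numbers run by site at about 4 sites, yet site is in no efficacy or imputation model and blocking is not stated: a possible small loss of precision, cheap to remove if the lists are blocked

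*SAP*

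**What the plan says.** **Allocation.** The Protocol synopsis plans "Approximately 4 investigative sites in the United States". Protocol 6.3 randomises subjects "by assignment of the lowest 4-digit randomization number available at the investigative site, starting with RXX01, where XX is a 2-digit site number". Protocol 8.6 repeats the site-coded numbering and adds: "No randomization numbers will be skipped or omitted". SAP 4.1, the section on the method of assignment, gives the 1:1 ratio but no block size, no stratification factor and no account of how the lists are generated. A randomisation schedule is planned as Listing 16.1.7, but it is an output of the study and is not supplied.

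**Analysis.** SAP 12.1 fits the primary ANCOVA at each time point "with the time appropriate post-CAC itching scores at Visit 4a as a covariate and treatment group as the sole factor", and Protocol 10.8 agrees. For the imputation, Protocol 10.7 says: "The model will include variables for treatment, baseline measure, and response measure". The PROC MI code in SAP 12.1 lists the same three variables. The repeated-measures model in SAP 12.1 has treatment, time and baseline. Protocol 10.9 describes the corresponding secondary models "with treatment, time point, and time appropriate baseline as covariates for adjustment". SAP 12.2.1 carries the primary method over to the key secondary visits. No analysis has a site term, and no site-adjusted sensitivity analysis appears among the planned tables.

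**The concern.** When allocation is arranged within groups, the analysis would normally include those groups. If the arms are balanced within site by blocking, differences between sites cancel out of the treatment comparison. A model without site still counts them as residual error. The estimated standard error is then larger than the true one, the confidence interval is too wide and the test is slightly conservative.

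At stake is the width of the interval for the primary itching comparison at Visit 6b and for the five key secondary visits. The validity of the comparison is not at stake. The gap in SAP 4.1 matters because, without knowing how the lists were built, a reader cannot tell whether the planned model matches the randomisation. That question is best settled while the study is masked, so that site adjustment is not chosen after the results are known.

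**Working it through.** **1. Reproduce the stated power.** Inputs from SAP 5: 40 per arm, SD 1.0, two-sided alpha 0.05, differences 0.87, 1.08 and 1.13.
- SE = 1.0 × √(2/40) = 0.2236.
- Noncentrality = difference / SE = 3.89, 4.83 and 5.05. With 78 df the critical value is 1.991.
- Power from the noncentral t = 97.0%, 99.8% and 99.9%. Joint power under independence is the product, 96.65%. The product of the three rounded figures is 96.7%.

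The plan's figures reproduce with no site term.

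**2. What the documents leave open.** They give neither the structure of the lists nor any between-site variance. Let *s* be the share of residual variance (after the Visit 4a score) that lies between sites. The values 0, 2, 5 and 10% are assumptions.

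**3. Lists blocked within site: formula.** Take four sites and SD 1.0 as the residual SD before site is removed.
- Planned model: 77 df (80 − 3), t = 1.9913, half-width = 1.9913 × 0.2236 = 0.445.
- Model with site: 74 df, t = 1.9925, half-width = 1.9925 × 0.2236 × √(1 − *s*).

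| *s* | SE with site | Half-width with site | Planned minus site | Planned CI relative to site CI |
|---|---|---|---|---|
| 0 | 0.2236 | 0.446 | −0.0003 | 0.1% narrower |
| 2% | 0.2214 | 0.441 | 0.004 | 0.9% wider |
| 5% | 0.2179 | 0.434 | 0.011 | 2.5% wider |
| 10% | 0.2121 | 0.423 | 0.023 | 5.3% wider |

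If the Visit 4a score lowers the residual SD below 1.0, the half-widths shrink in proportion and the percentages stay the same.

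**4. Lists blocked within site: simulation.** Trials of 80 subjects with one baseline covariate were simulated, with sites of 20/20/20/20 or 40/20/12/8 and with fixed or random site effects (40,000 runs per cell).
- The planned CI was 0.1% narrower at *s* = 0, then wider by 0.6 to 1.0%, 1.7 to 2.6% and 3.5 to 5.5%.
- The size of the planned test was about 0.050, then 0.046 to 0.048, 0.044 to 0.047 and 0.039 to 0.044.
- A version closer to the SAP used scores bounded at 0-4 in steps of 0.25, an assumed 10% missing, and 20 bounded and rounded imputations. It gave 0.1% narrower, then 1.1%, 2.7% and 5.4% wider, so bounding and imputation do not change the picture.
- In a separate simulation with blocks of 4, a true difference of 0.87 was estimated at 0.868 to 0.872 with or without site. Power at 3 minutes without and with site was 97.4% against 97.7% at *s* = 5%, and 97.8% against 98.2% at *s* = 10%.

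**5. Lists not blocked (simple randomisation).** The size of the planned test stayed near 0.05. Adding site changed the CI width by about +2.1% at *s* = 0, +1.0 to +1.4% at 2%, −0.6 to +0.4% at 5%, and −1.5 to −3.2% at 10%.

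**The case against.** The strongest reply is that no error has been shown. Protocol and SAP agree on a valid, pre-specified model, and leaving site out is defensible with about 4 sites and 80 subjects. Site effects on this endpoint may well be small: itching is rated by the subject on an anchored scale (Protocol Appendix I), one supplier provides and reconstitutes the allergens (Protocol 11.4), entry requires average itching of at least 3 at Visit 4a (Protocol 5.5.2), and the time-matched Visit 4a score is already a covariate. The 10% share has no support in the documents.

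All of this stands, and it limits the point to a small and conditional one. It does not remove it. If the lists are blocked, omitting site leaves the standard error essentially unchanged or overstated, and including it costs almost nothing.

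Four stronger readings are tempting, and the documents do not support them.
- **That the arms are balanced within site.** Site-coded numbering does not prove this. Protocol 9.9.2 says: "The envelopes and product will both be labeled with the same randomization number". The code may therefore serve supply and labelling only. Equally, blocking is unstated, which does not show that it is absent.
- **That the comparison is biased or the type I error inflated.** The difference is unbiased and the test is at worst conservative. For imputed data this also assumes that missingness does not depend on site differently in the two arms.
- **That the trial is underpowered.** The stated power reproduces without site.
- **That precision can be lost only under blocking.** Step 5 shows a gain of 1.5 to 3.2% from adding site at a 10% share without blocking. The necessary condition is residual variation between sites. Blocking decides whether the planned standard error is overstated or is valid but less efficient.

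**Conclusion.** The point holds as a cheap improvement. Allocation numbers run by site, site appears in no efficacy or imputation model, and blocking is not stated. Whether the plan loses any precision cannot be determined from the documents.

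With blocked lists, the loss ranges from nothing at a zero site share to an interval about 4 to 5% wider at an assumed 10% share, or roughly 0.02 units against a half-width of about 0.445. Without blocking, the planned analysis is valid as it stands, and adding site costs about 2% of CI width at a zero share, is about neutral at 5% and gains about 1.5 to 3% at 10%. These figures assume about four sites, 80 subjects and a residual SD of 1.0; the site shares are assumptions.

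**What to change.** Before unmasking:

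1. Confirm from the randomisation specification, without releasing allocations, whether the lists are blocked within site. State the answer in SAP 4.1.
2. **If blocked:**
   - Add SITE as a class factor to the itching ANCOVA (primary and key secondary), to the repeated-measures model and to the other endpoints analysed by ANCOVA.
   - Add site indicators to PROC MI. With four sites this means three indicators, and the MINIMUM, MAXIMUM and ROUND lists grow from three entries to six.
   - Set a rule for pooling very small sites that uses total site size only, so that it can be applied masked. For example, a site with fewer than 4 randomised subjects joins the next smallest; that threshold is a matter of choice.
   - Keep the planned no-site model as a sensitivity analysis.
   - Record the change in SAP 15, which now reports none.
3. **If not blocked:** keep the planned primary model. A pre-specified site-adjusted sensitivity analysis is optional.

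The t-tests, the Wilcoxon tests and the nasal composite tests can stay as planned. SAP 1 gives the SAP precedence over the protocol on statistical methods, so a SAP edit is enough. If the lists are blocked, the statistical cost is about 3 of 77 error df and a CI about 0.1% wider if sites do not differ. If they are not, the cost is the SAP 4.1 statement and, if wanted, one extra table.

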The following SAS code will then be used to combine results across imputations for the treatment means and differences respectively:

```
ODS OUTPUT PARAMETERESTIMATES = PE1;
PROC MIANALYZE DATA = LS;
BY VISIT TIME TREATMENT;
MODELEFFECTS ESTIMATE;
STDERR STDERR;
RUN;
ODS OUTPUT PARAMETERESTIMATES = PE2;
PROC MIANALYZE DATA = DIFF;
BY VISIT TIME TREATMENT;
MODELEFFECTS ESTIMATE;
STDERR STDERR;
RUN;
```

where the statement WHERE _TREATMENT=2 identifies the differences for active minus vehicle. The detailed code will be determined based on the final data.

Least squares means (LS Means) for each treatment, LS Means treatment differences and corresponding 95% CIs as estimated by the ANCOVA model will be provided.

In addition, ANCOVA models accounting for repeated measures will be run at Visit 6b as another supportive analysis. This ANCOVA model will include the time appropriate post-CAC itching scores at Visit 4a as a covariate and treatment group and time point as factors. The LS Means for each treatment, the LS Means treatment difference between OTX-DP and PV, and the corresponding 95% CIs will be calculated from these ANCOVA models. SAS pseudo-code for the ANCOVA model accounting for repeated measures at Visit 6 for multiply imputed data follows (Note: the same imputation routine described above [PROC MI \rightarrow PROC MIXED \rightarrow PROC MIANALYZE] will be employed using the below PROC MIXED pseudo-code):

```
PROC MIXED DATA=INDATA;
BY VISIT _IMPUTATION_;
CLASS SUBJID TREATMENT TIME;
MODEL SCORE = TREATMENT TIME BASELINE;
REPEATED TIME / SUBJECT=SUBJID TYPE=UN;
LSMEANS TREATMENT / PDIFF CL;
RUN;
```

where *INDATA* is the name of the input dataset sorted by *VISIT*, *_IMPUTATION_*, *SUBJID* and *TIME*.

An unstructured variance-covariance matrix will be used for the above repeated measures model. If the model does not converge using the unstructured matrix, the first order autoregressive structure and the compound symmetry structure will be employed, in that order.

Two-sample *t*-tests will also be used as unadjusted sensitivity analyses at each post-CAC time point, as well as non-parametric Wilcoxon rank sum tests for comparing OTX-DP and PV. Mean treatment differences, 95% CIs for each of the means, and 95% CIs for the mean differences will be presented for each post-CAC time point.

The following SAS code will be used for the t-test:

```
PROC TTEST DATA=INDATA;
BY VISIT TIME _IMPUTATION_;
CLASS TREATMENT;
VAR SCORE;

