ODS OUTPUT STATISTICS = OUTPUTDF;
RUN;
PROC MIANALYZE DATA = OUTPUTDF;
BY VISIT TIME CLASS;
MODELEFFECTS MEAN;
STDERR STDERR;
RUN;
```

The following SAS code will be used for the Wilcoxon rank sum test:

```
ODS OUTPUT WILCOXONSCORES = WILCOXON (WHERE=(CLASS=:"1"));
PROC NPAR1WAY DATA = INDATA WILCOXON;
    BY VISIT TIME IMPUTATION ;
    CLASS TREATMENT;
    VAR SCORE;
RUN;
DATA WILCOXON;
  SET WILCOXON;
  BY VISIT TIME;
  MEAN = (SUMOFSCORES - EXPECTEDSUM) /N;
  STDERR = STDDEVOFSUM/N;
RUN;
PROC MIANALYZE DATA = WILCOXON ALPHA = 0.05;
BY VISIT TIME;
MODELEFFECTS MEAN;
STDERR STDERR;
RUN;
```

The ordering of the above code should be adjusted accordingly for the real data, to make sure the tests are performed to compare the treatment group vs. the placebo group.

Sensitivity or supportive analyses will be performed on the ITT population using LOCF, BOCF, and WCO imputations as well as observed data only (see Section 8.2.1 for additional data imputation details). The primary analysis will also be repeated on the PP population with observed data only.

A line graph will be produced to show mean (+/- standard error [SE]) ocular itching score by treatment group (OTX-DP, PV), visit (Visit 6b, Visit 8b), and time point (3, 5, and 7 minutes post-CAC). Mean change from baseline (+/- SE) for each treatment arm will be presented in a similar figure. Both figures will be presented separately for the ITT population using observed data only.

A listing of ocular itching scores for all subjects will also be provided.

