12.2.2 Other Secondary Analyses

Other secondary efficacy variables include ocular itching at $10(\pm 1)$ minutes post-CAC at visits 5 (Day 7), 6a (Day 8), 7 (Day 14), 8a (Day 15), and 8b (Day 15; 8 hours from Visit 8a), and conjunctival redness, episcleral and ciliary redness, chemosis, eyelid swelling, tearing/watery eyes, rhinorrhea, nasal pruritus, ear or palate pruritus, and nasal congestion assessed at Visits 5 (Day 7), 6a (Day 8), 6b (Day 8; 8 hours from Visit 6a), 7 (Day 14), 8a (Day 15), and 8b (Day 15; 8 hours from Visit 8a) at 7(±1), 15(±1), and $20(\pm 3)$ minutes post-CAC. Scoring scales for each assessment are presented in Appendix A.

These secondary quantitative endpoints will be analyzed in a manner similar to the primary endpoint using the ITT and PP populations with observed data only. Note that ocular itching at 10(±1) minutes post-CAC will be analyzed together with the primary efficacy ocular itching scores (including imputing missing values) even though it is considered a secondary variable.

Additionally, a composite score of the presence or absence of at least one nasal symptom will be derived for each subject based on rhinorrhea, nasal pruritus, ear or palate pruritus, and nasal congestion scores. The composite score is "Present" if at least one nasal symptom is > 0, "Absent" if all symptoms are equal to zero, and missing if any symptoms are missing and the recorded symptoms are all equal to zero.

The nasal composite scores will be summarized using counts and percentages for each response category (present, absent, missing). Nasal composite scores will be analyzed using Fisher's exact tests and Cochran-Mantel-Haenszel tests (controlling for time-appropriate Visit 4a post-CAC nasal composite scores

and including just the "Present" and "Absent" categories) at each time point for each of Visits 5 (Day 7) through 8b (Day 15).

Nasal composite scores will also be summarized as a quantitative measure calculated as the sum of the four component symptom scores (ranging from 0 to 16). If any of the four component symptom scores is missing, then the quantitative composite score will be missing. Quantitative nasal composite scores will be summarized using quantitative descriptive statistics. A two-sample test will be used to compare treatment groups at each timepoint for each of Visits 5 (Day 7) through 8b (Day 15).

All secondary efficacy endpoints will be presented in separate listings.

13. Safety Analyses

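### Imputing each minute separately can make the standard error of the supportive Visit 6b repeated-measures analysis about 5% too small; the primary test is not affected

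*SAP*

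**What the plan says.** Protocol 10.7 sets the rule: "A separate imputation model will be fit for each time point". SAP 12.1 repeats it by visit: "A separate imputation model will be fit for each visit and time point". The code, which opens with "PROC MI DATA = INDATA SEED = 59411 NIMPUTE = 20 OUT", runs BY VISIT TIME with three variables: treatment, the Visit 4a score at the same minute, and the score being imputed. Draws are limited to 0-4 and rounded to 0.25. One seed is set for the whole run.

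SAP 12.1 then adds repeated-measures ANCOVA models that "will be run at Visit 6b as another supportive analysis". They use the same imputation routine, the statement "REPEATED TIME / SUBJECT=SUBJID TYPE=UN", and a single treatment effect across time points.

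The success rule is separate. Under SAP 8.5 a visit counts as significant only if all three time points are, and SAP 12.1 tests each with its own ANCOVA. The listed sensitivity and supportive analyses use "LOCF, BOCF, and WCO imputations as well as observed data only".

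**The concern.** The analysis model assumes that one subject's scores at 3, 5 and 7 minutes are correlated. The imputation model never sees two minutes together. That matters little if a single score is missing, but the protocol creates whole missing visits. A subject with only one insert left is not challenged (Protocol 7.8). A subject prescribed anti-inflammatory or anti-allergy medication is followed for safety only (Protocol 7.7).

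If the draws are independent across BY groups, two things follow. The completed data show too little within-subject correlation, which lowers the within-imputation variance of the time-averaged effect. The imputation noise also averages out over the three minutes, which lowers the between-imputation variance. Rubin's rules add the two, so the total is too small and the reported confidence interval and p-value look more precise than the data allow.

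SAP 12.1 names only Visit 6b for this model. However, its code runs BY VISIT, Protocol 10.9 plans "ANCOVA models which will be run at each visit, with treatment, time point, and time appropriate baseline as covariates", and SAP 12.2.1 carries the same imputation methods to the key secondary visits. If the imputed-data model is run there too, the same fault applies.

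**Working it through.** **Inputs from the documents.** 40 per arm, SD 1.0, differences 0.87 / 1.08 / 1.13, two-sided 0.05 (SAP 5); 20 imputations, limits, rounding and models (SAP 12.1).

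**The plan's own figures.** The noncentrality is d / (1.0 × √(2/40)) = d / 0.2236, that is 3.89, 4.83 and 5.05. With 78 df the power is 97.0%, 99.8% and 99.9%, with product 96.7%, as stated. The plan gives no standard error for the repeated-measures model.

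**Assumptions.** Missing fraction m: SAP 5 allows up to about 10 replacements, and 10/90 = 11%. That is a ceiling, so 5-20% is shown. Within-visit correlation r: 0.3-0.9.

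**Closed form** (many imputations, equal variances, common r, whole visit missing, no limits). Up to a common factor:

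- planned variance = [1 + 2r(1−m) + m/(1−m)] / 3
- correct variance = (1 + 2r) / [3(1−m)]

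At m = 1/9 and r = 0.8 the brackets are 1 + 1.422 + 0.125 = 2.547 and 2.6 × 1.125 = 2.925. The SE ratio is √(2.547/2.925) = 0.933, a shortfall of 6.7%. At r = 0.3, 0.5 and 0.9 it is 4.0%, 5.4% and 7.0%; at r = 0 it is zero. At r = 0.8 it is 3.0% with 5% missing and 11.8% with 20%.

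The complete-data bracket is 1 + 2r. The planned variance falls below it when r > 1/[2(1−m)], which is 0.56 at m = 1/9. Above that correlation, losing data appears to add precision.

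**Simulation with the SAP's limits and rounding.** Per arm, 2 of 40, 5 of 45 or 8 of 40 subjects miss the whole visit at random. Assumed: r = 0.8, Visit 6b vehicle mean 2.6, Visit 4a mean 3.3 with SD 0.5, correlation 0.4 between visits. REML fit with unstructured covariance; 4,000 replicates per row; no treatment effect.

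| Missing | SE planned | SE joint | SE observed only | SE complete | Planned SE / sampling SD | False positives: planned / joint / observed / complete |
|---|---|---|---|---|---|---|
| 5% | 0.176 | 0.181 | 0.183 | 0.179 | 0.97 | 6.5 / 5.8 / 5.4 / 5.4% |
| 11% | 0.164 | 0.173 | 0.179 | 0.169 | 0.93 | 7.2 / 6.1 / 5.7 / 5.3% |
| 20% | 0.170 | 0.188 | 0.200 | 0.179 | 0.90 | 8.0 / 6.1 / 5.9 / 5.6% |

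SEs are lower in the 11% row because it has 45 per arm. Monte Carlo error is about 0.35-0.4 points on a 5-6% rate.

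- Shortfall against joint imputation, from unrounded SEs: 2.5%, 5.4% and 9.5%. For r = 0.7 / 0.9 it is 5.0 / 6.1% at 11% missing and 8.7 / 10.6% at 20%. Without limits and rounding it is 4, 8 and 14%. With the 10-minute score also in the model, it is 6.2% at 11%.
- Variance components at 11%: within 0.0257 planned against 0.0278 joint; between 0.0012 against 0.0024. With 20 imputations the planned total is 0.0257 + 1.05 × 0.0012 = 0.0270, whose root is 0.164.
- A separately programmed run at 11% and r = 0.8 gave 0.163 planned, 0.173 joint, 0.179 observed only and 0.168 complete.
- If every BY group used the same random stream, the SEs would be 0.182, 0.176 and 0.194, with no shortfall.
- Primary ANCOVA per time point as planned: SE / sampling SD 0.97-1.02, rejection 4.6-5.9%.

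**The case against.** **Nothing is decided by this model.** It is supportive and outside the hierarchy. Putting the effect-scenario estimates beside the null-scenario SEs at 11% missing, planned is −0.970 / 0.164 (z about 5.9) and joint is −0.960 / 0.173 (z about 5.5). The 95% half-width moves from 0.32 to 0.34 on a scale scored in half units. This stands, and it is why the point is minor. The SAP still commits to reporting the interval, which should be valid.

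**An unaffected version may already be planned.** SAP 12.1 labels the repeated-measures code as being for multiply imputed data, calls the model supportive, and lists observed-data analyses among the sensitivity or supportive ones. Protocol 10.9 specifies observed data for the secondary endpoints just before it introduces these models. That reading is plausible, but no sentence says that the repeated-measures model will be fitted to observed data at Visit 6b.

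**The 5% is one cell of an assumed grid.** True. It depends on a missing rate and a correlation that the documents do not give, and on independent draws across BY groups. The direction is the same at every positive correlation examined under independent draws; only the size moves.

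**Joint imputation is not perfect.** With the limits kept, a whole set of scores is redrawn when one falls outside 0-4. The estimate moves slightly toward zero (complete data −0.986), and SE / SD is still 0.97 at 11%. Observed-data false-positive rates are at least as good. This stands and makes the observed-data fit an acceptable alternative.

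**Conclusion.** The concern holds, as a minor point. As written, the imputation omits a correlation that the supportive repeated-measures model uses. At 11% missing and correlation 0.8 the reported SE is about 5% below that from joint imputation and about 7% below the estimator's true sampling SD. It is also below the SE with no data missing. The range against joint imputation is 2.5% to 9.5% for 5-20% missing at that correlation.

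This rests on assumed missing rates and correlations, on subjects missing the whole visit at random, and on independent draws across BY groups. The SAP does not state that last condition and should not depend on it. The primary decision is unaffected, because each per-time-point ANCOVA uses the same variables as its imputation model and its SE is sound.

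**What to change.** Before unmasking, put the data in wide format, drop BY TIME, and impute the 3-, 5-, 7- and 10-minute scores of a visit together. The model would hold treatment, the four Visit 4a scores and the four scores of that visit (9 variables), BY VISIT, with 20 imputations, the limits and the rounding kept. The 10-minute score belongs there because SAP 12.2.2 says it "will be analyzed together with the primary efficacy ocular itching scores (including imputing missing values". Run the repeated-measures model on these datasets. Alternatively, state that this model will be fitted to observed data.

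The per-time-point ANCOVA can stay on the planned datasets, so that the decision analysis does not change. If it moved to the joint ones, power for all three time points would be 98.0% against 98.4% at 11% missing, and 94.8% against 95.8% at 20%. Omitting the limits in the joint run gives 98.2% and 95.6%.

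The cost is a few lines of SAP text and code and no new data. Because Protocol 10.7 prescribes separate models, SAP section 15, which now reports no changes from the protocol, needs an entry. Keeping the primary on its planned datasets means maintaining two imputed sets. The 9-variable model ran without failure in simulation at 80-90 subjects; it should be tried in PROC MI itself. With the limits kept, the repeated-measures estimate moves slightly toward zero: −0.960 against −0.970 planned at 11% missing, and −0.937 against −0.955 at 20%.
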